13.3.1.3 Body surface area involvement

The total BSA affected by psoriasis will be assessed.

Assessment at screening is performed by a trained investigator. Assessment at baseline (2) and follow-up (visit 3 and 4) will be performed by a blinded assessor only.

13.3.1.4 Quantitative nail assessment

The total number of nails affected by psoriasis will be assessed. The nails are assessed for both nail matrix psoriasis and nail bed psoriasis. Features of nail matrix psoriasis includes nail pitting, leukonychia, red spots in the lunula, and crumbling of the nail. Features of nail bed psoriasis includes onycholysis, oil drop (salmon patch), dyschromia, splinter hemorrhages, and nail bed hyperkeratosis.

Assessment at screening is performed by a trained investigator. Assessment at baseline (visit 2) and follow-up (visit 3 and 4) will be performed by a blinded assessor only.

13.3.1.5 Quantitative joint assessment

Joints are palpated for the purpose of determining if they are tender and/or swollen, the latter implying the presence of active synovitis, and both implying the presence of inflammation.⁵⁷ Joint swelling is defined as soft tissue swelling of the joint which is detectable along the joint margins. A synovial effusion invariably means that the joint is swollen. Fluctuance is a characteristic feature of swollen joints; neither bony enlargement nor deformity of the joint

Trial ID (EudraCT No.): 2017-003697-14	Date: 23.02.2018	Page Version 2.3
---	------------------	---------------------

constitutes “swelling”. Joint swelling may influence the range of joint motion, which can be useful to recognize the presence of swelling.⁵⁸

Joint tenderness is defined as pain at rest that is induced by pressure at examination of some joints such as the metacarpophalangeal (MCP) and wrist joints. The assessor should use his/her thumb and index finger to exert pressure that is sufficient to cause whitening in the assessors nailbed, which is called the “rule of thumb”.⁵⁸

The total number of swollen and the total number of tender joints will be recorded.

13.3.2 Subject assessments

13.3.2.1 Dermatology Life Quality Index

The Dermatology Life Quality Index (DLQI) is a validated questionnaire with content specific to those with dermatology conditions. It consists of 10 items addressing the subject's perception of the impact of their skin disease on different aspects of their quality of life (QoL) over the last week such as dermatology-related symptoms and feelings, daily activities, leisure, work or school, personal relationships, and the treatment.⁵⁹ Each item is scored on a 4 point Likert scale (0 = not at all /not relevant; 1 = a little; 2 = a lot; 3 = very much). The total score is the sum of the 10 items (0 to 30); a high score is indicative of a poor QoL. The DLQI will be completed according to the Schedule of procedures in Section 7 and at each self-injection during home-use of the investigational medicinal product. The DLQI is included in the appendix.

13.3.2.2 Psoriasis Symptom Inventory (PSI)

The Psoriasis Symptom Inventory (PSI) is an eight-item psoriasis-specific, patient-reported outcome measure used in assessing the severity of psoriasis symptoms.⁶⁰ The PSI has demonstrated excellent internal consistency, test-retest reliability, validity, and responsiveness in moderate to severe plaque psoriasis, based on a pooled analysis of data from a phase II clinical study (n = 198) to evaluate the efficacy of brodalumab in moderate to severe chronic plaque psoriasis.⁶¹ The PSI consists of 8 items: itching, redness, scaling, burning, stinging, cracking, flaking, and pain. Patients were asked to complete the 24-hour and 7-day recall version of the PSI by rating the severity of each symptom on a 5-point categorical rating scale, ranging from not at all to very severe. The PSI can use a 24-hour recall and 7-day recall, and both versions have been found to yield comparable data.⁶⁰ A PSI total score is defined for each version as the sum of all 8 items and ranges from 0–32, with higher scores indicating greater severity.

The PSI will be completed according to the Schedule of procedures in Section 7 and at each self-injection during home-use of the investigational medicinal product. The PSI is included in the appendix.

13.3.2.3 Visual Analog Scale for joint pain

Trial ID (EudraCT No.): 2017-003697-14	Date: 23.02.2018	Page Version 2.3
---	------------------	---------------------

The pain is a unidimensional measure of pain intensity, which has been widely used in diverse adult populations, including those with rheumatic diseases.

A subjective assessment of the average joint pain over the last 3 days/ nights is recorded by the subject on a visual analogue scale, where 0 is no pain and 100 is the worst imaginable joint pain.

13.4 Clinical and laboratory assessments

13.4.1 Physical examination

A thorough physical examination of the subject including whole body inspection of the skin and auscultation of heart, lungs and abdomen; palpation of the abdominal organs and basic neurological status will be performed at the screening visit.

Height, weight, hip circumference, blood pressure, and pulse will be assessed according to the Schedule of procedures in Section 6.

Blood pressure and pulse (vital signs) will be measured in supine position following at least 5 minutes rest.

If an abnormal vital sign at screening is considered by the investigator to be clinically significant, it will be up to the investigator's discretion if the subject should be randomized into the trial.

In case of abnormal findings, the vital sign measurement can be repeated approximately 15 minutes later with subjects resting in a supine position to verify the first measurement. Should the repeated measurement result in a normal value, the measurement must be repeated once more. If the third measurement verifies the second (normal) value, the first measurement will be considered as false. If the third measurement confirms the first measurement (abnormal) the second measurement will be considered as false. Only the last value measured and considered as correct will be recorded in the eCRF.

13.4.2 Pregnancy test

A urine pregnancy test (human chorionic gonadotropin; dipstick) will be performed at the trial site at screening prior to randomization in female subjects of child-bearing potential.

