UVA: Ultraviolet type A
UVB: Ultraviolet type B
VAS: Visual analog scale
VOI: Volume of interest

6 Flow diagram of trial design

Trial ID (EudraCT No.): 2017-003697-14	Date: 23.02.2018	Page Version 2.3
---	------------------	---------------------

7 Schedule of procedures

Visit	Screen 1	Visit 2	Visit 3	Visit 4
Week	-4	0	6	16
Office visits				
Informed consent	X			
Demographics	X			
Inclusion/exclusion criteria	X			
Diagnosis of PsA	X			
Smoking/alcohol consumption	X			
Psoriasis: medical history / previous psoriasis therapies	X			
Other medical history / treatments	X			
Concomitant medications	X	X		X
Randomization	X			
Collection of adverse events			X	X
Physical examination				
General physical examination	X			X
Height	X			
Weight	X			X
Hip circumference	X			
Blood pressure, pulse	X			X
PASI	X	X	X	X
BSA	X	X	X	X
IGA	X	X	X	X
Quantitative nail assessment	X	X	X	X
Quantitative joint assessment	X	X	X	
DLQI	X	X	X	X
PSI	X	X	X	X
VAS (joints)	X	X	X	X
Labs				
Serum electrolytes + renal panel	X	X	X	X
Acute-phase proteins	X	X	X	X
Lipids	X	X		X
Liver enzymes	X	X		X
Glucose metabolism	X	X	X	X
T-spot	X			
HIV I+II	X			
Hepatitis serology	X			
Treatment				
Initiation of treatment / placebo		X		
Procedures				
FDG-PET/CT		X		X
Chest X-ray	X			
Optional punch biopsy		X	X	

Trial ID (EudraCT No.): 2017-003697-14	Date: 23.02.2018	Page Version 2.3
---	------------------	---------------------

Trial ID (EudraCT No.): 2017-003697-14	Date: 23.02.2018	Page Version 2.3
---	------------------	---------------------

8 Introduction, background, and rationale

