8.10 Ethical considerations

The study is conducted in compliance with the principles of the Declaration of Helsinki. No children or other vulnerable subjects incapable of giving informed consent will be enrolled in this clinical trial. Furthermore, women who are pregnant, breastfeeding, or trying to become pregnant will not be enrolled in this clinical trial. Women of child-bearing potential have to agree to use a highly effective method of contraception to prevent pregnancy during the clinical trial. In addition, all female subjects of child-bearing potential will have a pregnancy test performed before treatment and study related procedures are commenced. Only psoriasis patients will be enrolled, meaning that only patient who may benefit from the results obtained in this trial is participating.

Subjects are not reimbursed for participating in the trial, meaning that financial motivation will not lead to impaired judgment.

The risk of developing solid cancers follows a linear pattern with increasing dose although the age at which exposure takes place is highly relevant. A decline in radiosensitivity does take place with age, making young individuals more susceptible to radiation-induced malignancies. Although the malignancy risk for the population as a whole is 5 %/Sv, this is higher in children and considerably lower in older individuals.

The exposure to radiation restricts the age groups that may be enrolled to individuals > 40 years of age to reduce the stochastic risk of malignancies. Furthermore, by choosing this age-cutoff the study will include patients that may potentially benefit from incidental PET findings. Cardiovascular comorbidity and premature atherosclerotic disease associated with psoriasis are relevant for this age group. Younger individuals more susceptible to radiation-induced malignancies and with low absolute risk of incidental malignant findings and cardiovascular disease are excluded from participation. Moreover, the typical mean age of

Trial ID (EudraCT No.): 2017-003697-14	Date: 23.02.2018	Page Version 2.3
---	------------------	---------------------

patients with moderate-to-severe psoriasis included in clinical trials is approximately 40-50 years.

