20. Major surgery within the past 3 months.
21. Pregnancy or lactation (Women of childbearing potential must use a highly effective* form of birth control (confirmed by the investigator) throughout the trial and until 12 weeks after discontinuation of treatment with brodalumab).
22. Claustrophobia.
23. Reduced renal function (serum creatinine > 200 µmol/L or cr-EDTA clearance < 30 ml/min)
24. Any disorder, including but not limited to, cardiovascular, lung, gastrointestinal, hepatic, renal, neurological, musculoskeletal, infectious, endocrine, metabolic, haematological, immunological, psychiatric, or major physical impairment that is not stable, in the opinion of the investigator, and could:
 - Affect the safety of the subject throughout the trial.
 - Influence the findings of the trial or their interpretations.
 - Impede the subject's ability to complete the entire duration of trial.

* A highly effective method of birth control is defined as one which results in a low failure rate (less than 1% per year) such as bilateral tubal occlusion, intrauterine device (IUD), intrauterine hormone-releasing system (IUS), combined (estrogen and progestogen containing) hormonal contraception associated with inhibition of ovulation (oral, intravaginal, transdermal), progestogen-only hormonal contraception associated with inhibition of ovulation (oral, injectable, implantable), sexual abstinence (when this is in line with the preferred and usual life style of the subject), vasectomised partner (given that the subject is monogamous). The subjects must have used the contraceptive method continuously for at least 1 month prior to the pregnancy test. A female is defined as not being of child bearing potential if she is postmenopausal (at least 12 months with no menses without an alternative medical cause prior to screening), or surgically sterile (hysterectomy, bilateral salpingectomy or bilateral oophorectomy).

Trial ID (EudraCT No.): 2017-003697-14	Date: 23.02.2018	Page Version 2.3
---	------------------	---------------------

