13.1 Overview

Protocol approval (Danish Medicines Agency and Ethical Committee): by November 2017
First patient first visit: December 2017

Patient enrollment and investigational procedures: December 2017 – April 2019

Last patient last visit: April 2019

Data collection completion: May 2019

Data analysis and publication of results: Until January 2020

Evaluations to be done at each visit are shown in the schedule of procedures in Section 7. Refer to Section 10.1 for further details on the trial design.

During the course of the trial, subjects may need to be seen at unscheduled visits. The assessments to be performed at an unscheduled visit are left to the investigator's discretion. Assessment of psoriasis disease severity (PASI, IGA, BSA, nail count, and joint count) after randomization will be performed only by the blinded assessor.

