13.2 Assessments performed only at screening/baseline

Assessments performed only at the screening and/or baseline visit include: assessment of

Trial ID (EudraCT No.): 2017-003697-14	Date: 23.02.2018	Page Version 2.3
---	------------------	---------------------

elegibility criteria, demographics, medical history, height, and weight. These are described in further detail below. Laboratory tests include hepatitis B, hepatitis C, HIV-1, HIV-2, T-spot, and serum pregnancy test. Varicella zoster antibody analysis may be relevant in some subjects. Procedures include chest X-ray.

A pre-treatment chart is completed before initiation of treatment according to national guidelines (Appendix III)

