13.4.3 Laboratory testing

The following analyses will be performed at the Biochemical laboratory Aarhus University Hospital: Sodium, Potassium, Creatinine, C-reactive protein, Alkaline phosphatase, Alanine aminotransferase, Gamma glutamyl transferase, Cholesterol, LDL cholesterol, HDL cholesterol. Triglycerides, Glucose (non-fasting), Hba1c, Albumin, Hemoglobin, Leukocytes, Neutrophils, (neutrophils/total cells), Lymphocytes (lymphocytes/total cells) Monocytes (monocytes/total cells), Eosinophils (eosinophils/total cells), Basophils (basophils/total cells), Thrombocytes, Urinalysis (Protein, Glucose, Ketones, Occult blood, Leukocytes, Nitrite).

Trial ID (EudraCT No.): 2017-003697-14	Date: 23.02.2018	Page Version 2.3
---	------------------	---------------------

Analysis of hepatitis serology and HIV 1+2 will be performed according to institutional protocols. Analysis of varicella zoster antibodies will be performed in case of no history of previous varicella zoster infection. These tests are standard procedures before commencing treatment with biologic agents.

A sample of 4 mL blood in an EDTA-tube is collected for storage at visit 1 (screening) and visit 3 (week 6). Plasma is separated from erythrocytes by centrifugation and stored at -150°C for later analysis of inflammatory markers.

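### Sections 13.2 and 13.4.2 name different pregnancy tests, and the text shown ties no test to either FDG injection

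*Protocol*

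**What the plan says.** Four places in the protocol bear on the pregnancy test.

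- Section 13.4.2 fixes specimen and visit: "A urine pregnancy test (human chorionic gonadotropin; dipstick) will be performed at the trial site at screening prior to randomization". It applies to women of child-bearing potential.
- Section 13.2 opens with "Assessments performed only at the screening and/or baseline visit include" and then gives a list of laboratory tests ending in "HIV-1, HIV-2, T-spot, and serum pregnancy test".
- Section 8.10 says that women of child-bearing potential will "have a pregnancy test performed before treatment and study related procedures are commenced". It names no specimen, no visit and no maximum age for the result.
- The contraception footnote to exclusion 21 in Section 11.3 speaks of a single test: "The subjects must have used the contraceptive method continuously for at least 1 month prior to the pregnancy test".

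Section 13.1 sends the reader to the schedule: "Evaluations to be done at each visit are shown in the schedule of procedures in Section 7". That schedule has rows for T-spot, HIV, "Hepatitis serology" and chest X-ray, but none for a pregnancy test. It places screening at week -4, visit 2 at week 0 and visit 4 at week 16, with FDG-PET/CT at visits 2 and 4. Under Section 12.2 the first dose follows the baseline scan at visit 2.

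**The concern.** Two things look wrong. The first is a plain inconsistency: one section asks for a urine dipstick at the site, the other for a serum test. Neither refers to the other or calls itself confirmatory, and the schedule does not settle which is meant.

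The second is timing. Pregnancy is an exclusion, and Section 8.9 calls radiation exposure the main risk of the study. Yet the only test with a fixed visit is at screening, four weeks before the first FDG injection. The preparation steps in 13.5.1 and the glucose check in 13.5.3 include no pregnancy check on the day of the scan. At stake is fetal exposure to radiation, or to brodalumab, that a test on the day could have prevented. Estimation and testing of the endpoints do not depend on this.

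**Working it through.** The protocol states no figure on this point to reproduce. The check compares the passages and then counts weeks.

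**Specimen.** 13.4.2 says urine; 13.2 says serum; 8.10 and the footnote to exclusion 21 say neither. A single test cannot satisfy both 13.4.2 and 13.2. Either one of them is wrong, or two tests are intended and the protocol does not say so.

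**Timing.** 13.4.2 fixes screening. 13.2 permits screening or baseline, so baseline is allowed but not required, and its restriction to those visits leaves no test at week 16. 8.10 is met by any test done before treatment and study procedures. The condition in 13.4.2 that the test precede randomization does not tie it to visit 2 either: Section 12.3 puts randomization at visit 2, whereas Section 7 marks it in the screening column. Section 12.3 requires that no exclusion criterion be violated at that point but asks for no new test.

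**Age of the result**, from the nominal weeks in Section 7:

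| Last test | At first FDG injection and first dose (week 0) | At second FDG injection (week 16) |
|---|---|---|
| Screening, week -4 | 0 - (-4) = 4 weeks | 16 - (-4) = 20 weeks |
| Baseline, week 0 (allowed by 13.2, not required) | 0 weeks | 16 - 0 = 16 weeks |

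Section 12.2 allows a scan to be rescheduled, and 12.7.5 allows the final visit to be postponed after a treatment interruption. Either can lengthen the gap.

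**Size of the risk.** The one documentary input is the failure rate in the footnote to exclusion 21, under 1% per year. Spread evenly over the year and taken at its limit, the chance of conception between the screening test and the first scan is 1% x 4/52 = 0.077%, or about 0.08% per woman. Two assumptions enter: an even weekly rate, and use of contraception good enough for the stated rate to hold. The age limit of 40 in Section 11.2 points to a lower risk, but the protocol gives no figure by which to adjust.

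**The case against.** The strongest case on the other side is that most of the protection is already in place. Pregnancy is an exclusion. The investigator must confirm highly effective contraception, to be used throughout the trial and for 12 weeks after brodalumab stops, and it must have been in use for at least a month before the test. Subjects are 40 or older, and 8.10 requires a test before treatment. No passage promises repeat testing, so its absence contradicts nothing. All of this stands, and it is why the risk is low and the point is minor. It does not settle the specimen, and contraception is not a test result.

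Four stronger readings are tempting, but the documents do not support them.

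- A reader might infer that one screening test satisfies every passage. It meets the timing wording of all of them, but one specimen cannot be both urine and serum. The two sections could also be read together as a site dipstick plus a serum test, with the serum test possibly at visit 2.
- A reader might infer that nothing at all requires a current result at the first FDG injection. Section 13.2 calls for a pre-treatment chart (Appendix III), which is not shown and may contain such a check. The claim can be made only for the text shown.
- A reader might take the missing schedule row, and the absence of hCG from 13.4.3 (whose urinalysis list is "Urinalysis (Protein, Glucose, Ketones, Occult blood, Leukocytes, Nitrite"), as proof that the serum test is a slip. Both are weak evidence. Varicella antibody, which like the pregnancy test applies only to some subjects, also has no row in Section 7. T-spot is absent from 13.4.3 although 13.2 and Section 7 require it.
- A reader might scale the per-woman figure up to a probability for the whole trial and call it an upper bound. The protocol does not give the number of women of child-bearing potential or the period in which a dipstick misses an early pregnancy, and poorer adherence to contraception would raise the figure. It states no fetal dose either, so none can be claimed.

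**Conclusion.** The concern holds as a minor inconsistency together with a cheap safety improvement. Sections 13.2 and 13.4.2 disagree on specimen, and the schedule that should resolve this is silent. Subject to what Appendix III may add at visit 2, the protocol can be followed with a result about 4 weeks old at the first FDG injection and first dose. At the second FDG injection the result would be about 16 to 20 weeks old.

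The risk is at most about 0.08% per woman between screening and the first scan, provided the contraceptive failure rate in exclusion 21 holds in practice and is even over time. The case for change rests on how little a current result would cost at two visits that already take place. The primary and secondary endpoints and their analysis are untouched.

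**What to change.** Name one test, a urine hCG dipstick, in both 13.2 and 13.4.2. Add a pregnancy-test row to Section 7 for women of child-bearing potential, with three entries:

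- screening;
- visit 2, with a negative result before FDG injection and first dose;
- visit 4, with a negative result before FDG injection.

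The visit 2 test guards against the first radiation exposure and against starting brodalumab in pregnancy. The visit 4 test guards only against the second radiation exposure, since treatment has been given by then. If Appendix III already requires a visit 2 test, the row should simply agree with it.

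The cost is two extra dipsticks per woman of child-bearing potential and a wait of a few minutes each time. No added visit or invasive procedure is needed.

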13.4.3 Laboratory testing

The following analyses will be performed at the Biochemical laboratory Aarhus University Hospital: Sodium, Potassium, Creatinine, C-reactive protein, Alkaline phosphatase, Alanine aminotransferase, Gamma glutamyl transferase, Cholesterol, LDL cholesterol, HDL cholesterol. Triglycerides, Glucose (non-fasting), Hba1c, Albumin, Hemoglobin, Leukocytes, Neutrophils, (neutrophils/total cells), Lymphocytes (lymphocytes/total cells) Monocytes (monocytes/total cells), Eosinophils (eosinophils/total cells), Basophils (basophils/total cells), Thrombocytes, Urinalysis (Protein, Glucose, Ketones, Occult blood, Leukocytes, Nitrite).

Trial ID (EudraCT No.): 2017-003697-14	Date: 23.02.2018	Page Version 2.3
---	------------------	---------------------

Analysis of hepatitis serology and HIV 1+2 will be performed according to institutional protocols. Analysis of varicella zoster antibodies will be performed in case of no history of previous varicella zoster infection. These tests are standard procedures before commencing treatment with biologic agents.

A sample of 4 mL blood in an EDTA-tube is collected for storage at visit 1 (screening) and visit 3 (week 6). Plasma is separated from erythrocytes by centrifugation and stored at -150°C for later analysis of inflammatory markers.

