
brodalumab treated psoriasis subjects compared to placebo and whether this change is associated with changes in skin inflammation.
 
To assess the change in soluble inflammatory biomarkers from baseline to week 16 in brodalumab treated psoriasis subjects compared to placebo.
 
To assess whether the change in aortic wall inflammation and/or splenic inflammation is associated with psoriasis-specific genotypes.
 
To assess the change in gene expression and cytokine expression in paired lesional and non-lesional psoriatic skin from baseline to week 16 in brodalumab treated psoriasis subjects compared to placebo.
	
 subcutaneous adipose tissue from baseline to week 16 Association between change in PASI and change in subcutaneous adipose tissue MeanSUV_{max}. Changes in acute phase proteins from baseline to week 16 Correlation between changes in both aortic meanTBR_{max} and SLR and presence of HLA-B*08, HLA-C*06:02, HLA-B*27, HLA-B*38 and HLA-B*39 Changes in gene expression and cytokine expression in skin samples from baseline to week 16 Correlation with changes in mean aortic TBR_{max} and SLR.
---	---

10 Trial design

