11.3 Exclusion criteria

1. Non-Danish speaking
2. Known or suspected allergy or reaction to any component of the IMP formulation.
3. History of inflammatory bowel disease, arthritis (not including psoriatic arthritis), systemic lupus erythematosus, and active inflammatory skin diseases.
4. A history of malignancies within the past five years (excluding localized non-melanoma skin cancer).
5. Topical corticosteroid treatment (class III or stronger) and/or ultraviolet type B phototherapy within 2 weeks prior to randomization
6. Treatment with psoralen plus ultraviolet type A photochemotherapy, methotrexate, cyclosporine, acitretin, or fumaric acid esters within 4 weeks prior to randomization.
7. Treatment with adalimumab, etanercept, infliximab, cosentyx, or ixekizumab within 12 weeks, ustekinumab within 24 weeks, or other immunosuppressive or anti-inflammatory agents within 5 half-lives of the active substance prior to the FDG-PET/CT, respectively.
8. Scheduled surgery during the trial period (expect minor minimally invasive procedures).
9. Systemic infection or fever within 7 days prior to FDG-PET/CT.
10. Severe obesity (> 150 kg due to a PET/CT scanner limitation).

Trial ID (EudraCT No.): 2017-003697-14	Date: 23.02.2018	Page Version 2.3
---	------------------	---------------------

11. Presence of uncontrolled diabetes mellitus (HbA1c > 75 mmol/mol and/or blood sugar > 11.1 mmol/l and/or clinical judgment).
12. History of coagulation defects (clinical judgment).
13. Active or latent tuberculosis requiring treatment.
14. Positive hepatitis B surface antigen (HBsAg), hepatitis B surface antibody (HBsAb), hepatitis B core antibody (HBcAb) or hepatitis C virus antibody (anti-HCV) serology at screening. Subjects with positive HBsAb may be randomised provided they are hepatitis B vaccinated and have negative HBsAg and HBcAb.
15. History of any known primary immunodeficiency disorder including a positive human immunodeficiency virus (HIV) test at screening, or the subject taking antiretroviral medications as determined by medical history and/or subject's verbal report.
16. No history of varicella zoster infection and negative varicella antibody test (until varicella vaccination is completed).
17. History of chronic alcohol or drug abuse within 12 months prior to screening, or any condition associated with poor compliance as judged by the investigator.
18. History of intravenous drug use.
19. History of attempted suicide or is at significant risk of suicide.

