13.4.5 Research biobank

Samples of plasma (4 mL) are collected for storage in a research biobank at visit 1 (screening) and visit 3 (week 6). Optional skin punch biopsies are collected at baseline and visit 3 (week 6).

Purpose of the research biobank is to store the biological material safely until analysis of inflammatory markers can be performed in all samples.

Termination of the research biobank: January 2020.

Any remaining biological materials after this date will be anonymized or destroyed.

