15.4.3 Analysis of other endpoints

Change in acute phase proteins at week 16 between groups and change in abdominal subcutaneous adipose tissue FDG-uptake will be analysed using a repeated measures model. Changes in cytokine expression and gene expression in optional skin samples will be analysed using a repeated measures model. Association between change in PASI and change in subcutaneous adipose tissue as well as the association between change in TBR/SLR and psoriasis-specific genotypes will be computed using applicable correlation coefficients.

Trial ID (EudraCT No.): 2017-003697-14	Date: 23.02.2018	Page Version 2.3
---	------------------	---------------------

16

REFERENCES

2. Christophers E. Psoriasis – epidemiology and clinical spectrum. *Clinical and Experimental Dermatology*. 2001;26(4):314-320.
3. Bowcock AM. The genetics of psoriasis and autoimmunity. *Annu Rev Genomics Hum Genet*. 2005;6:93-122.

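### Plasma stored for inflammatory markers is drawn at screening and week 6, so any marker measured only in it cannot show the baseline-to-week-16 change in the Section 9.1 objective

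*Protocol*

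**What the plan says.** The objective in Section 9.1 reads: "To assess the change in soluble inflammatory biomarkers from baseline to week 16 in brodalumab treated psoriasis subjects compared to placebo". The endpoint that fits it in the same table is "Changes in acute phase proteins from baseline to week 16", and Section 15.4.3 plans the matching analysis, "Change in acute phase proteins at week 16 between groups", with a repeated measures model. The schedule in Section 7 marks the row "Acute-phase proteins" at all four visits (weeks -4, 0, 6 and 16).

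The stored plasma follows a different timetable. Section 13.4.3 says "A sample of 4 mL blood in an EDTA-tube is collected for storage at visit 1 (screening) and visit 3 (week 6"), and that the plasma is "stored at -150°C for later analysis of inflammatory markers". Section 13.4.5 repeats the times: "Samples of plasma (4 mL) are collected for storage in a research biobank at visit 1 (screening) and visit 3 (week 6"). The Section 7 schedule has no row for plasma storage, so nothing there adds a tube at week 0 or week 16.

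Section 12.3 places randomisation at baseline, visit 2. Section 12.2 gives the first dose at visit 2, after the baseline scan. Section 10.1 describes a washout before the study for subjects who need one. One of the limits in Section 11.3 is: "Treatment with psoralen plus ultraviolet type A photochemotherapy, methotrexate, cyclosporine, acitretin, or fumaric acid esters within 4 weeks prior to randomization".

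**The concern.** The objective is worded broadly, as soluble inflammatory biomarkers, and the biobank exists so that inflammatory markers can be measured later. A reader would expect the stored plasma to serve that objective for markers beyond the routine laboratory panel. Its sampling times do not allow this: there is no tube at the start of the interval and none at the end.

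The screening tube has a second weakness. Several washout limits count back from visit 2, so a subject can still be on prior therapy, or have only just stopped it, when that tube is drawn. The pre-treatment value then need not describe the untreated state in which the subject starts trial treatment.

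At stake is the usefulness of the biobank for an additional secondary objective. The loss is permanent, since a plan written later can change the analysis but not the sampling.

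**Working it through.** No figure in the protocol needs reproducing. The check compares sampling times.

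**Visit weeks (Section 7).** Screening = week -4, visit 2 = week 0, visit 3 = week 6, visit 4 = week 16.

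**Weeks needed against weeks sampled**

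| Material | Weeks needed | Weeks sampled | Missing |
|---|---|---|---|
| Acute phase proteins (routine) | 0, 16 | -4, 0, 6, 16 | none |
| Stored plasma | 0, 16 | -4, 6 | 0 and 16 |

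**Could screening count as baseline?** Section 12.3 equates baseline with visit 2. Section 13.4.5 also keeps the terms apart, placing plasma at screening and biopsies at baseline. Even if screening were accepted as baseline, week 16 would still be missing.

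**What the two tubes measure.** Let Y(t) be a marker at week t.

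- Objective: Y(16) - Y(0) = [Y(6) - Y(0)] + [Y(16) - Y(6)].
- Available: Y(6) - Y(-4) = [Y(6) - Y(0)] + [Y(0) - Y(-4)].

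The two share only the first bracket. The change from week 6 to week 16 is never observed. The available change includes a segment before treatment that the objective does not contain.

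- Interval covered: 6 - (-4) = 10 weeks, of which 4 precede the first dose and 6 follow it.
- Share of the treatment period covered: 6/16 = 37.5%.

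**Washout at the screening tube (Section 11.3, with randomisation and scan at week 0).**

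- Exclusion 5 (UVB, class III or stronger topical corticosteroids): 2 weeks before randomisation, so use up to week -2 is compatible with it, after the tube is drawn.
- Exclusion 6 (PUVA and the conventional systemic agents): 4 weeks before randomisation, so use up to about the day of the tube is compatible.
- Exclusion 7 (named biologics): 12 or 24 weeks before the scan, so at week -4 a subject may be 12 - 4 = 8 or 24 - 4 = 20 weeks into washout.

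This applies to some subjects only. Washout is conditional on need, and Section 11.5 allows re-screening once it is complete. The protocol does not give the proportion affected.

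**Effect on the comparison between arms.** The segment Y(0) - Y(-4) lies wholly before the first dose. Under randomisation its expected value is the same in both arms, so it cancels from the expected difference. Its spread between subjects does not cancel. It adds variance to a comparison of 25 per arm (Section 10.2). The amount cannot be computed, because the protocol gives no standard deviations for these markers. Within an arm nothing cancels, so the change mixes withdrawal of prior therapy with six weeks of trial treatment.

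**One ambiguity.** The schedule as extracted marks randomisation at screening, against visit 2 in Section 12.3. If screening were right, the limits in exclusions 5 and 6 would end there and the washout point would weaken for those therapies. The missing weeks 0 and 16 would be unchanged.

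**The case against.** The strongest reply is that the objective can be answered as the protocol puts it into practice. Its listed endpoint is acute phase proteins, these are scheduled at weeks 0 and 16, C-reactive protein is among the routine tests in Section 13.4.3, and Section 15.4.3 analyses that change. This stands. A reader might infer that the biomarker objective is left without data; the documents do not support that.

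Second, no passage ties the stored tube to the week-16 objective, and neither Section 9.1 nor 15.4 lists an endpoint or analysis for stored-plasma markers. The link is inferred from the breadth of the objective and the stated purpose of the biobank. This also stands, and it is why the point is confined to further markers measured in stored plasma.

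Third, a week-6 plasma sample is coherent in itself. It coincides with the follow-up skin biopsy (Section 13.4.4) and supports a valid randomised comparison at week 6. That argues for keeping the tube, but it does not supply week 16.

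Three further readings go beyond the text:

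- That the screening tube is contaminated in every subject needing washout. Someone who stopped early, or was re-screened after washout, may be clear of prior therapy.
- That washout confounds the treatment comparison. Randomisation balances prior-therapy withdrawal between arms in expectation, so the cost is noise, not systematic bias.
- That a planned correlation of plasma markers with aortic uptake or the spleen-to-liver ratio fails. The correlation bullet in Section 9.1 follows the skin-expression endpoint, and no passage plans such an analysis for plasma.

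**Conclusion.** The point holds in a limited form. Markers that depend on stored plasma have neither a week-0 nor a week-16 sample, and two sections agree on the times, so this is not a slip in one line. For those markers only a change from week -4 to week 6 is available, with 6 of 16 treatment weeks covered. The first sample can reflect prior therapy in an unknown share of subjects.

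The acute phase protein endpoint, the primary endpoint and the sample size are not affected. The conclusion assumes that baseline means visit 2, as Section 12.3 states, and that the stored plasma is meant to contribute to the soluble-biomarker objective. The missing time points do not depend on the washout argument, which is secondary.

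This should be changed, because the loss cannot be repaired later and the correction is cheap. Section 13.4.5 also closes the biobank in January 2020, after which remaining material is anonymised or destroyed.

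**What to change.** In Sections 13.4.3 and 13.4.5:

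- move the screening storage tube to visit 2, before the first dose;
- add a 4 mL storage tube at visit 4 (week 16);
- keep the week-6 tube, which matches the follow-up biopsy.

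Add a plasma-storage row to the Section 7 schedule showing visits 2, 3 and 4. Stored plasma would then exist at weeks 0, 6 and 16, which contains both weeks the objective needs.

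Cost: stored blood per subject rises from 2 x 4 = 8 mL to 3 x 4 = 12 mL, one extra 4 mL tube. Blood is already drawn at visits 2 and 4, so no visit or venepuncture is added. The pre-washout sample is lost, but no listed endpoint uses it.

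If tubes have already been collected on the present timetable, Section 9.1 should state that stored-plasma markers are compared from screening to week 6. That removes the inconsistency, but it answers a different question from the one the objective poses.
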